Comparing EEG patterns in different age groups during general anesthesia with sevoflurane.

NTC number: NCT03559504

Date: 28/7/2018

Comparing EEG patterns in different age groups during general anesthesia with sevoflurane.

Background

Analyzing the raw electroencephalography (EEG) waves during anesthesia is still challenging and has not been fully demonstrated. Alterations of consciousness are due to effects of anesthetic agents that act on the central nervous system, more precisely, on the brain. These alterations are major clinical endpoints of general anesthesia and can be analyzed and monitored throughout recordings of surface brain electrical activity, called electroencephalography (EEG). EEG is a powerful tool that refers to the recording of the brain's spontaneous electrical activity along the scalp and it can be used to measure voltage fluctuations which result from ionic current flows within neurons found in the brain. The electroencephalogram is increasingly used to measure anesthetic drug effect on the central nervous system. Since, analyzing the real-time raw electroencephalographic signal during anesthesia is difficult, several electroencephalographic monitors have been developed to extract and process information and to present the content in a continuous index from 0 to 100. Zero represents the deepest level of anesthesia (isoelectric encephalographic line), and 100 represents the awake state of a patient. The use of electroencephalographic monitors has been proven to decrease drug consumption during anesthesia and to lead to a faster recovery from anesthesia. Recently, the use of the Bispectral Index® (BIS®) monitor (Aspect Medical Systems, Newton, MA) has been shown to decrease the incidence of intraoperative awareness. Depth of anesthesia is frequently assessed using electroencephalogram processing systems, such as BIS and M-Entropy® (Datex-Ohmeda, Helsinki, Finland). The use of these monitors has been claimed to allow more accurate drug administration which has the theoretical benefit of avoiding phases of too light or too profound anesthesia and the associated risks of hemodynamic instability. Inadequate general anesthesia caused by under dosage causes intraoperative awareness whereas prolonged anesthesia increases the risk of postoperative complications because of over dosage. The most important factor that contributes to the inadequate general anesthesia is the current limited ability to determine the level of awareness. In this study, we want to

analyze the raw EEG waves under general anesthesia using sevoflurane of MAC 1.0 for different age groups from 0 to 80 years old.

Like other organ systems, the nervous system is functionally immature at birth, myelination is rapid during the first 2 years and completed by 7 years of age.ⁱ Therefore, the BIS algorithm cannot automatically be extrapolated to young children. Some investigations suggest that BIS may be valid in children older than 2 years of age.ⁱⁱ Only one study, as far as we know, evaluated prospectively the correlation of BIS with end-tidal sevoflurane concentration in children. Regarding the effect of age on BIS values, there have been reports comparing the BIS between infants and children or between children and adultsⁱⁱⁱ but there have been no reports comparing the raw EEG waves in all age groups (0-80 years old) under sevoflurane of 1.0 MAC. Minimal alveolar concentration (MAC) was introduced to compare the potencies of inhalation anesthetic agents. Sevoflurane is a commonly used inhalation anesthesia agent today. However, the relation between concentration of 1.0 MAC sevoflurane and raw EEG states in different age groups is relatively unstudied. In this prospective randomized study we want to know if there is any correlation of brain waves under general anesthesia in different age groups. It is therefore of neuroscientific interest to assess whether the electroencephalographic correlates of sevoflurane-induced unconsciousness have different or similar frequency range among the age groups.

General anesthetic and sedative agents induce highly structured oscillations in the EEG.^{iv} There is growing evidence that these oscillations relate directly to the systems-level mechanisms by which anesthetics produce altered states of consciousness. During normal brain function, oscillations regulate the timing and coordination of brain activity within and between functional systems and circuits. Anesthesia induced oscillations are thought to disrupt this coordinated activity, producing different states of altered arousal depending upon the receptors and circuits upon which the drugs act.^v General anesthesia with sevoflurane is characterized in the EEG by frontally coherent alpha (8–12 Hz), delta (1–4 Hz), and high amplitude slow (0.1–1Hz) oscillations.^{vi} This pattern, observed when adult patients are sufficiently anaesthetized to conduct surgery, is similar to that observed under propofol-induced general anesthesia and suggests a common systems-level mechanism of action.^{vii} Given that the brain rapidly develops and undergoes significant changes from

childbirth into adulthood, anesthesia induced EEG oscillations in children might differ from those of adults, and could vary significantly with age. Characterizing the structure of the EEG in relation to age would help establish the foundations for age-appropriate monitoring of brain states during general anesthesia and sedation in children. We aimed to examine the effects of age on the EEG during general anesthesia, with sevoflurane as the sole hypnotic agent. The EEG is typically described in terms of rhythmic activity and transients. The rhythmic activity is divided into bands by frequency (figure 1 and figure 3).

Objective

Aim:

This study is designed to evaluate the correlation of raw EEG patterns and age under 1.0 MAC sevoflurane.

Study design and purpose

This study is being conducted to evaluate and assess the electroencephalography wave patterns in different age patients undergoing surgery under general anesthesia. The aim of our study is to compare the raw EEG waves in different age patients and analyze any changes in these patterns among various age groups and which of these groups will have the EEG signal of high-frequency waves or low frequency waves. Previous studies have shown that light sedation is often accompanied by decreasing posterior alpha waves and increasing the intensity of frontal/central beta waves.

Sample size: 120

Based on 6 different age groups from infants to elderly (0-80 years old), we are recruiting 120 patients with an American Society of Anesthesiology score (ASA) I or II, scheduled for elective surgery under general anesthesia lasting less than 2 hours. Each group will have 20 cases.

Methods:

A sample of 120 healthy patients from the Second Affiliated Hospital of Wenzhou Medical University with American Society of Anesthesiologists (ASA) physical status I or II will be randomly selected and included in this study. After obtaining ethical approval and written informed consent, we will enroll 120 patients (ASA I and II), aged 0-80 years of either gender undergoing minor elective surgery. The selected patients will be divided into 6 different groups according to their age (figure 2). The surgeries will last less than two hours each and will be performed under general anesthesia which is an indispensable part of surgery. Depth of anesthesia and electrical brain activity will be monitored using Bispectral index monitoring system. However, these are based on the underlying changes in the features of an EEG signal as the signals vary with the level of anesthesia. We will compare the different EEG waves (alpha, delta, theta and gamma) for all age patients while maintaining 1.0 MAC sevoflurane. Data related to non-invasive blood pressure, heart rate, respiration rate, oxygen saturation, EEG waves frequencies, end tidal volume of sevoflurane and BIS values will be recorded. These data will be analyzed every 1 min for the first 10mins during maintenance of anesthesia with 1.0 MAC sevoflurane. Data collection will be first recorded after tracheal intubation. The raw EEG wave will be recorded by means of a Universal Serial Bus (USB) which will later be analyzed and processed offline.

120 patients undergoing minor elective surgeries will be allocated in 6 age groups: 1month-1 year old (infant period), 1-3 years old (toddler period), 3-6 years old (preschool age period), 7-18 years old (school age period), 18-65 years old (adults) and 65-80 years old (elderly). After arrival in the operating room, an intravenous line will be inserted into a large forearm vein, and standard monitors will be applied. Each patient will be continuously monitored by a 3-lead electrocardiogram, noninvasive arterial pressure, pulse oximetry, and end-tidal carbon dioxide concentration. In addition to the standard conventional monitors, BIS electrodes will be placed before induction on each patient. The electroencephalogram will be recorded continuously over a period of 10 minutes using the Aspect A-2000 BIS®monitor (version XP). All the 120 patients enrolled in this study will be studied for 10 minutes after induction and tracheal intubation without any surgical stimulus. After the skin of the forehead had been prepared and cleaned with

alcohol, the BIS® (BIS-XP sensor) and BIS electrodes will be positioned as recommended by the manufacturers. Anesthesia will be induced by sevoflurane inhalation only with a tight-fitting facemask and a 4-l airflow of 100% oxygen. As spontaneous breathing diminishes, patients will be manually assisted and with cessation of spontaneous breathing, will be mechanically ventilated via the facemask to an end-tidal carbon dioxide of 35 mmHg. The induction of anesthesia will be the same in all age groups and will consist of sufentanil 0.2-0.3mcg/kg or fentanyl 1-2 mcg/kg before intubation and 0.2 mg/kg cisatracurium to facilitate intubation. Sevoflurane inhalation will be adjusted in all age groups to maintain 1.0 MAC concentration. After tracheal intubation, patients will be ventilated with a tidal volume of 6-8 ml/kg and the respiratory rate will be adapted to obtain an end-tidal carbon dioxide concentration of 30–35 mmHg. After intubation, sevoflurane will be titrated to generate an end-tidal concentration (ETsevo) of 2.0, 3.0, and 4.0% in a stepwise increase or decrease pattern in each age group to maintain 1.0 MAC concentration.

All patients will be ventilated using an Ohmeda-Datex anesthetic machine with soda lime (CO₂ absorber). Hypotension, defined as a decrease in blood pressure by 25% from baseline, will be treated with intravenous fluid or phenyl ephedrine (20 microgram bolus). Raw EEG data, BIS values and end target expiratory concentration of sevoflurane will be recorded every one minute for a period of 10 mins after induction and intubation. Raw EEG data (figure4-patient of 80 years old), will be analyzed and processed using the pdf screenshot from the BIS vista monitor. The pdf screenshots of the raw EEG will be recorded by means of a Universal Serial Bus (USB). The pdf screenshots will be taken twice during the 10 minutes of recording to minimize any loss of data.

Inclusion Criteria:

Patients age between 0 to 80 years old, ASA I or II scheduled for minor surgeries under general anesthesia lasting less than 2 hours each.

Exclusion Criteria:

Potential subjects with any neurologic or psychiatric disease, relative or absolute contraindication to sevoflurane including pregnancy by patient self-report, and any recent

prescription or illicit medication use will be excluded. Patients with a history of any disabling central nervous or cerebrovascular disease and patients who had received central nervous system-active drugs will be excluded from the study. We will exclude patients with poor quality data, most likely because of poor electrode contact.

Potential benefits

The advantages of this study are to help the anesthesiologist have a better understanding of the brain waves under general anesthesia. EEG monitoring provides assessment of brain perfusion during state of general anesthesia. Brain death during anesthesia can be assessed and prevented with the use of raw EEG patterns.

EEG waves monitoring is a key aspect in preventing brain damage and ensuring the level of anesthesia is within the required range.

Maintaining the required range of deep anesthesia (BIS value of 40 to 60) helps avoid the incidence of awareness with recall in adults during general anesthesia and sedation.

Potential risks

There are no risks and complications associated with this study. However, mild redness may appear on the forehead in some patients from the BIS electrodes.

Statistics:

Statistical analyses will be performed with a statistical package (SPSS version 21.0; SPSS, Chicago, IL) and Microsoft excel. All data will be presented as mean \pm sd.

Demographic data will be compared by using standard t-tests; comparison of incidence data between groups performed by using Fisher's exact tests. A P value < 0.05 will be considered significant.

Study duration:

We are estimating that the entire study will require one year, including patient recruitment, data collection, data analysis and report writing.

Co-Investigators:

Name	Department	Role
[name]	Anesthesiology, The second affiliated hospital of Wenzhou Medical University.	Principal Investigator
[name]	Anesthesiology, The second affiliated hospital of Wenzhou Medical University.	Co-Clinical Investigator

Payment:

There is no financial benefit or any reimbursement for participation in this study.

Figure 1:

Band	Frequency (Hz)
Delta	< 4
Theta	≥ 4 and < 8
Alpha	≥ 8 and < 14
Beta	≥ 14

Figure 2:

Groups	Age
1- Infant period	1month-1 year old
2- Toddler period	1-3 years old
3- Preschool age period	3-6 years old
4- School age period	7-18 years old
5- Adults	18-65 years old
6- Elderly	65-80 years old

Figure 3:

[figure not shown]
[figure not shown]

Figure 4:

References:

ⁱ Prashant J. General growth and tissue development throughout childhood. In: Bruno B, Bernard JD, eds. *Pediatric Anesthesia: Principles and Practice*. New York: McGraw-Hill, 2002; 32–3

ⁱⁱ McCann ME, Bacsik J, Davidson A, Auble S, Sullivan L, Laussen P. The correlation of bispectral index with endtidal sevoflurane concentration and haemodynamic parameters in preschoolers. *Paediatr Anaesth* 2002; 12: 519–25

ⁱⁱⁱ Davidson AJ, McCann ME, Devavaram P, et al. The differences in the bispectral index between infants and children during emergence from anesthesia after circumcision surgery. *Anesth Analg* 2001; 93: 326–30

^{iv} Gibbs FA, Gibbs LE, Lennox WG. Effects on the electroencephalogram of certain drugs which influence nervous activity. *Arch Intern Med* 1937; 60: 154–66

^v Lewis LD, Weiner VS, Mukamel EA, et al. Rapid fragmentation of neuronal networks at the onset of propofol-induced unconsciousness. *Proc Natl Acad Sci USA* 2012; 109: E3377–8

^{vi} Brown EN, Solt K, Purdon PL, Akeju O. Monitoring Brain State During General Anesthesia and Sedation. *Miller's Anesthesia*: Philadelphia: Elsevier, 2014 (Chapter 50)

^{vii} Brown EN, Lydic R, Schiff ND. General anesthesia, sleep, and coma. *The New England Journal of Medicine* 2010; 363:2638–50

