**STATISTICAL PLAN:**

Statistical analyses will be performed with a statistical package (SPSS version 21.0; SPSS, Chicago, IL) and Microsoft excel. All data will be presented as mean  $\pm$  sd. Demographic data will be compared by using standard t-tests; comparison of incidence data between groups performed by using Fisher's exact tests. A P value  $< 0.05$  will be considered significant.

Data related to non-invasive blood pressure, heart rate, respiration rate, oxygen saturation, EEG waves frequencies, end tidal volume of sevoflurane and BIS values will be recorded. These data will be analyzed every 1min for the first 10mins during maintenance of anesthesia with 1.0 MAC sevoflurane. Data collection will be first recorded after tracheal intubation. The raw EEG wave will be recorded by means of a Universal Serial Bus (USB) which will later be analyzed and processed offline.

EEG waves , BIS values and Et sevoflurane will be collected every 1minute for a period of 10 minutes at T1,T2,T3,T4,T5,T6,T7,T8,T9,T10.

Non-invasive blood pressure, heart rate, respiration rate and oxygen saturation values will be recorded every 3 minutes for the same period (10minutes).

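### The question is how EEG frequency varies with age, but waves are compared in bands fixed for all ages and the recorded frequency item is undefined, so a frequency shift can be misread as gain or loss of a rhythm, or missed

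*Protocol*

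**What the plan says.** **The question.** The Protocol Background asks whether the EEG correlates of sevoflurane unconsciousness "have different or similar frequency range among the age groups", and expects that "anesthesia induced EEG oscillations in children might differ from those of adults, and could vary significantly with age". Study design and purpose asks "which of these groups will have the EEG signal of high-frequency waves or low frequency waves".

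**The comparison.** Methods states it by named wave: "We will compare the different EEG waves (alpha, delta, theta and gamma) for all age patients while maintaining 1.0 MAC sevoflurane". The Background links waves to bands: "The rhythmic activity is divided into bands by frequency (figure 1 and figure 3"). Figure 1 sets delta below 4 Hz, theta from 4 to below 8, alpha from 8 to below 14, and beta from 14 upward, with no limits specific to age. Figure 3 is not reproduced in the text available.

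**The frequency item.** Methods also says "EEG waves frequencies, end tidal volume of sevoflurane and BIS values will be recorded", and the SAP repeats this. Neither document says whether the item is a number in Hz or a band label, or how it is derived. The SAP adds "All data will be presented as mean" with SD. It names t-tests for demographics and Fisher's exact test for incidence data, but no test for an EEG measure.

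**Band definitions.** They do not agree. The Background gives "frontally coherent alpha (8–12 Hz), delta (1–4 Hz), and high amplitude slow (0.1–1Hz) oscillations", whereas alpha in Figure 1 runs to 14 Hz. Methods lists gamma and omits beta; Figure 1 has beta and no gamma.

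**The concern.** The amount of activity in a fixed band depends on two things: how strong a rhythm is, and where its peak lies relative to the edges. The protocol itself expects age to alter the oscillations. If age moves the peak, band amounts change although the rhythm is equally strong.

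The age conclusion can then go wrong in two ways. A report that the young have theta and the old have alpha may describe one rhythm displaced by 1 or 2 Hz. A report of no age difference in alpha may conceal a change in frequency, which is what the study asks about. Correcting how band power is calculated, or moving the edges, does not cure this: any fixed set of bands behaves this way when the peak can move.

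**Working it through.** **Inputs from the documents.** Band edges of 4, 8 and 14 Hz (Figure 1); the alternative alpha range of 8–12 Hz (Background); 20 patients in each of 6 groups (Sample size); significance at P < 0.05 (SAP). The total agrees, 6 × 20 = 120, but no effect size, SD or power is given, so there is no sample-size calculation to reproduce.

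**Assumptions, not from the documents.** A single spectral peak, Gaussian in frequency with centre m and width s, and the same total power at every age. No background activity or measurement noise. Two-sided tests.

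**Step 1: a shift across 8 Hz.** Alpha share = Φ((14 − m)/s) − Φ((8 − m)/s). With s = 1:

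- m = 7: Φ(7) − Φ(1) = 1.000 − 0.841 = 0.159
- m = 9: Φ(5) − Φ(−1) = 1.000 − 0.159 = 0.841

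The share goes from 16% to 84% with no change in strength. With s = 0.7 it goes from 8% to 92%, and with s = 1.5 from 25% to 75%. A 1 Hz move, 7.5 to 8.5 Hz, gives 16% to 84% at s = 0.5, 31% to 69% at s = 1 and 40% to 60% at s = 2. Relabelling is therefore near complete only for a narrow peak or a dominant-band label, and partial for a broad peak.

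**Step 2: a shift inside 8 to 14 Hz.** The midpoint is 11 Hz, and two peaks equally far from it have the same alpha share. For 9.5 and 12.5 Hz at s = 1:

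- m = 9.5: Φ(4.5) − Φ(−1.5) = 0.933
- m = 12.5: Φ(1.5) − Φ(−4.5) = 0.933

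The neighbouring bands do move. At s = 1, theta share goes from 0.067 to 0.000 and beta from 0.000 to 0.067. At s = 2, theta goes from 0.22 to 0.01 and beta from 0.01 to 0.23.

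**Step 3: what a 20 v 20 comparison would show.** Simulated t-tests, 4,000 trials per pair, s = 1, between-patient SD of peak frequency 1 Hz. Percentage of trials significant:

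| Peak centres | Alpha share | Theta and beta shares | Peak frequency |
|---|---|---|---|
| 9.5 v 12.5 Hz | about 5% | about 100% each | about 100% |
| 10 v 12 Hz | about 5% | about 93% each | about 100% |

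Both pairs are symmetric about 11 Hz. Away from that symmetry, alpha share itself responds: 75% of trials for 9 v 12 Hz and 99% for 9 v 11 Hz. In the 9.5 v 12.5 Hz case the mean theta share falls from about 14% to 0.1%, although the rhythm is no weaker.

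**Step 4: if only the dominant band is recorded.** Compare 7.5 with 8.5 Hz, 20 per group. For numeric frequency, power = Φ(1/(SD·√(2/20)) − 1.96). At SD 1 this is Φ(3.16 − 1.96) = 0.89; at SD 1.5 and 2 it is 0.56 and 0.35. Comparing the proportions labelled alpha (0.31 v 0.69 at SD 1) gives power of 0.69, 0.37 and 0.23 at the same three SDs.

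**Step 5: the other alpha range.** With 8–12 Hz and s = 1, the 9.5 to 12.5 Hz move changes alpha share from 0.93 to 0.31, so it is visible. The midpoint becomes 10 Hz, and 9 v 11 Hz is then hidden: Φ(3) − Φ(−1) = Φ(1) − Φ(−3) = 0.84. The 8 Hz edge is the same in both ranges, so Step 1 is unaffected.

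**The case against.** A reader might infer that frequency is compared only through bands, so that a shift of several Hz inside alpha could not be seen at all. The documents do not support that.

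- **A frequency item is listed.** Both documents record it and analyse it each minute, and all data are to be given as mean and SD. If it is a number in Hz, a shift inside alpha is measured directly. This stands. It limits the point to saying that the item is undefined; an undefined item is not a planned safeguard.
- **Other bands respond.** In the model of Step 3, theta and beta shares pick up the shift that alpha share misses, and theta is on the Methods list. This also stands, so no claim of invisibility can be made. But the result would read as theta lost, or as beta gained in a band the Methods list omits, when only the frequency had changed.
- **The hidden cases are special.** They need near-symmetry about the middle of the band. This stands; they are not typical of shifts inside alpha.
- **The bands are unsettled.** The alpha range differs between sections, Figure 3 is not available, and no EEG measure or test is named, so band share as the outcome is an assumption.
- **Common bands have value.** They allow comparison across ages. Peak frequency should supplement them, not replace them.

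**Conclusion.** The point holds in limited form. The study asks about frequency by age, states its comparison by named wave with one band table for all ages, and leaves its recorded frequency item without definition or unit.

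The edge effect at 8 Hz is the firmer half: a 2 Hz move at constant strength changes the alpha share from 16% to 84%, or from 25% to 75% with the broader peak. Inside 8 to 14 Hz the shift may be missed in alpha or misread through its neighbours, but it is not generally undetectable.

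All of these sizes rest on an assumed noise-free Gaussian peak, an assumed between-patient SD and assumed shifts. The documents give no expected age shift, so the figures show how the measure behaves and do not predict the trial's result. The matter should be corrected because it bears on the main age conclusion.

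**What to change.** In Protocol Methods and the SAP, define the EEG frequency item as two numbers per patient and epoch: the frequency in Hz, and the height above background, of the largest spectral peak in one pre-set range that spans 8 Hz. Allow a no-peak result. Name the analysis of peak frequency against age and report it beside the band results. Describe a theta or alpha difference as gain or loss of a rhythm only when peak height changes; when the peak crosses 8 Hz at similar height, report a shift in frequency. Settle one alpha range, and make the Methods wave list agree with Figure 1.

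**Cost.** SAP wording and one further derived measure, with no extra patients. Some recordings will show no clear peak, and the plan must say how these are counted.

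The digital EEG must also be kept. Methods describes a continuous 10-minute recording and raw EEG saved by USB for offline processing, but later says the EEG will be analysed from PDF screenshots taken twice in the 10 minutes. These must be reconciled. If only screenshots are stored, the fix also requires a change in data capture.

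### Induction is described as sevoflurane only and identical at every age, yet opioid drug and dose are left open and unrecorded, so any age-related difference in opioid use would enter the EEG-age comparison unseen

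*Protocol*

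**What the plan says.** The stated aim (Protocol, Objective) is: "This study is designed to evaluate the correlation of raw EEG patterns and age under 1.0 MAC sevoflurane". There are six age groups of 20 patients.

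The Methods section describes induction in two ways. The first is: "Anesthesia will be induced by sevoflurane inhalation only with a tight-fitting facemask". A little later it says: "The induction of anesthesia will be the same in all age groups and will consist of sufentanil 0.2-0.3mcg/kg or fentanyl 1-2 mcg/kg before intubation", followed by cisatracurium. Neither document says how the choice between the two opioids is made, how the dose within each range is set, or how either is kept comparable across age groups.

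On the recording window, Methods says: "All the 120 patients enrolled in this study will be studied for 10 minutes after induction and tracheal intubation without any surgical stimulus". The SAP places the readings at ten one-minute points, T1 to T10.

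The lists of recorded data (Protocol, Methods; SAP, Statistical Plan) cover vital signs, EEG, BIS and end-tidal sevoflurane. Opioid drug, dose and time of administration are not listed. The statistics text in both documents names t-tests for demographic data and Fisher's exact tests for incidence data. It mentions no covariate or stratification, and it names no test or model for EEG or BIS by age. Part of the SAP was not available for this review, so these statements about what is absent cover only the available text.

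**The concern.** Age cannot be randomised. Reading an EEG difference as an age effect therefore depends on the other exposures being alike across groups or being measured. The plan fixes sevoflurane at 1.0 MAC for this reason, but leaves a second centrally acting drug open in both identity and dose, given shortly before the window in which the outcome is measured.

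If anesthesiologists happen to favour one opioid, or one end of a dose range, at certain ages, the age contrast also carries an opioid contrast. With no opioid data in the study record, the investigators could neither see this nor adjust for it, and a report that induction was the same at all ages could not be checked against the study's own data.

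**Working it through.** **Consistency of the text.** Two statements in Methods do not fit the opioid sentence as written.

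- Sevoflurane alone, against an induction that is said to consist of an opioid and a muscle relaxant.
- Identical at all ages, against a choice of two drugs over ranges. The sufentanil range is 0.3/0.2 = 1.5-fold and the fentanyl range is 2/1 = 2-fold.

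**The plan's own figure.** 6 groups × 20 = 120, which agrees with the stated sample size. The plan gives no effect size, SD or power, so there is nothing further to reproduce.

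**Size of a possible distortion.** The inputs are:

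- n = 20 per group (Protocol, Sample size).
- Significance level 0.05 (both documents). Two-sided is assumed, since sidedness is not stated.
- p, the difference between two age groups in the share given one of the two opioids. Assumed: 0, 0.25, 0.60 (for example 80% against 20%) or 1.
- e, the difference between the opioids on an EEG measure, in SD units. Assumed: 0.3, 0.5 or 0.8. The documents give no value.
- No true age effect, and a two-sample t-test for one pair of groups. The test is also assumed, because the available text names none for EEG or BIS.

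Formulas: bias b = p × e. Noncentrality = b × √(n/2) = b × √10 = 3.162b. The false-positive rate is the probability that a noncentral t with 38 degrees of freedom falls outside ±2.024.

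Worked example: p = 0.60 and e = 0.5 give b = 0.30 SD and noncentrality 0.949, so the rate is 15.2%.

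| Imbalance p | e = 0.3 SD | e = 0.5 SD | e = 0.8 SD |
|---|---|---|---|
| 0 | 5.0% | 5.0% | 5.0% |
| 0.25 | 5.6% | 6.7% | 9.5% |
| 0.60 | 8.6% | 15.2% | 31.6% |
| 1 (complete separation) | 15.2% | 33.8% | 69.3% |

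The calculation leaves out the extra within-group variance that comes from mixing two opioids. Including it at p = 0.60 changes little: about 15% at 0.5 SD and about 29% at 0.8 SD. The dose ranges within each drug are not modelled.

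**The case against.** The strongest defence is that both statements have a sensible reading. Sevoflurane alone may mean that no intravenous hypnotic is used. The Background supports this, since it speaks of the study being done "with sevoflurane as the sole hypnotic agent", which leaves room for an analgesic adjunct. Likewise, identical induction may mean that the same options and the same per-kg ranges apply at every age. Nothing in Methods ties drug or dose to age.

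Most of this stands. A reader might take the sole-hypnotic wording as a further contradiction, but it is compatible with an opioid given as an adjunct. A reader might also infer a conflict with the Exclusion Criteria, which say "patients who had received central nervous system-active drugs will be excluded from the study". That sentence concerns medication before the study, not drugs given as part of the study anesthetic; read the other way, it would bar sevoflurane itself. Neither should be cited as a contradiction.

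The defence does not close the gap. Even on the generous reading, a common menu is not a common exposure: two age groups can both comply with Methods and still differ in drug and dose. The sentence also still says that induction consists of the opioid, so the wording needs repair.

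It is also fair to object that the available text names no model for EEG or BIS by age, and that this is the larger gap. Adjustment for opioid exposure can only be specified as part of whatever model is chosen.

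**Conclusion.** The point holds as one of inconsistent wording and of unmeasured, unbalanced exposure. Methods leaves opioid drug and dose open while calling induction uniform, and the available text contains no means of detecting or handling a difference across age groups.

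A reader might go further and infer that the age comparison is confounded. The documents do not support that: they neither show nor prevent an age-related pattern of opioid use, and they give no figure for how the two opioids differ on the EEG.

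The size is therefore a sensitivity range and not an estimate. It runs from no inflation (5.0%) when opioid use is balanced to about 69% for one pairwise comparison when use separates completely by age and the opioids differ by 0.8 SD. The range rests on the assumed imbalance, opioid difference, t-test and two-sided level set out above. The interval from opioid to first reading is not stated either, so how strongly the opioid acts during the window is unknown. The remedy is cheap enough to be worth making without proof of imbalance.

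**What to change.** 1. The sponsor should reconcile the induction statements in Methods so that they describe one regimen. Which drug or dose is used is a clinical decision, and none is proposed here.
2. Add three fields per patient to the recorded data: opioid given, dose in mcg/kg, and minutes from opioid to T1. Tabulate them by age group.
3. Once a model for EEG and BIS across age groups is named, report the age comparison both unadjusted and adjusted for opioid drug and for dose within drug. Dose needs drug-specific terms: the sufentanil and fentanyl ranges are not on a common mcg/kg scale, so one slope across both would be meaningless. With linear dose terms this takes 3 degrees of freedom (1 for drug, 2 for dose).
4. State in advance that if opioid choice almost fully tracks age, adjustment cannot separate the two effects and the conclusion must say so.

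The cost is a few fields from the anesthetic chart and a few degrees of freedom out of 120 patients. The intervals for the age effect will widen if opioid choice correlates with age.
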